#### **7.3.3 Extent and Maintenance of Blinding**

This is a double-blind study in which the IV inebilizumab and IV placebo are matching in appearance.

The Sponsor will remain blinded until after the database lock for primary efficacy analysis, which will occur after all subjects have completed Week 26 or discontinued early from the study. After Week 26, the AChR-Ab+ subjects who haven't completed the RCP will complete the remaining visits during the RCP per protocol. The Sponsor personnel who are directly associated with the conduct of the study will remain blinded to the treatment assignment until all subjects have completed the RCP or discontinued early from RCP. Subjects, site staff, and contract research organization (CRO) personnel will not be unblinded to individual subject treatment assignment until the completion of the study, except as specified herein. Prior to the completion of the study, individual treatment assignment may be revealed to the site and/or subject as required by the sponsor for execution of business activities; such unblinding is anticipated to be infrequent and will in no circumstance occur prior to the subject having completed at least 1 year in the OLP or exited the study.

Potentially unblinding laboratory data will not be available to the sites until after treatment assignments are unblinded to sites. The potentially unblinding laboratory results include B-cell counts and [REDACTED] after randomization up to and including the OLP Day 15 visit. Investigators and treating physicians must not request potentially unblinding laboratory results at a local laboratory.

If treatment allocation for a subject becomes known to the Investigator or other study staff involved in the management of study subjects, the Sponsor must be notified immediately.

#### **7.3.4 Unblinding Procedures**

In the event of a medical emergency, the Investigator may unblind an individual subject's IP allocation. Instructions for unblinding an individual subject's IP allocation are contained in the IXRS Manual. In general, unblinding should only occur if management of the medical emergency would be different based on the subject having received IP. In the majority of cases, the management of a medical emergency would be the same whether or not IP was received by the subject. If this was the case, the IP allocation should not be unblinded. In non-emergency situations where unblinding is being considered, the site should discuss the situation with a study medical monitor.

If a site unblinds the treatment assignment for a subject while in the RCP, the IP must be discontinued for that subject. The subject should remain in the study and complete all study assessments except those directly related to dosing.

#### **7.4 Assessment and Verification of Compliance**

Site staff will administer all IPs IV at the study center. The dose and date of administration of the IP must be recorded in the subject's eCRF. Treatment compliance will be assessed based on this information.

#### **7.5 Concomitant Medications and Treatments**

Subjects should receive all medications that are considered by their physician to be necessary for their health and well-being except for the medications that are specifically prohibited in [Section 7.5.2](#).

All concomitant medications given to the subject during the study will be recorded on the source document, including the start and stop dates, route of administration, and reason for administration.

The Sponsor recommends that Investigators ensure that all subjects are up to date with required vaccinations prior to entry into the study.

### **7.5.1 Immunosuppressive Medications During the Screening Period**

Azathioprine, mycophenolate mofetil, or mycophenolic acid can be used during the screening period; the dose can be lowered but cannot be increased during the 4 weeks prior to randomization. The same applies for tacrolimus (allowed in Japan only).

Corticosteroids can be used during the screening period; the dose can be lowered but it cannot be increased within 4 weeks prior to randomization.

Acetylcholinesterase inhibitors (pyridostigmine dose  $\leq$  480 mg/day) can be used during screening, but the dose must be stable for 2 weeks prior to randomization.

### **7.5.2 Prohibited Medications and Treatments**

Subjects receiving corticosteroids at the time of randomization will stay at the same corticosteroid dose (prednisone or its derivatives), and dose tapering will begin at Week 4 of the RCP. The maximum allowed dose of prednisone at the time of randomization will be 40 mg/day or 80 mg every other day. The corticosteroid dose must not have been increased within the 4 weeks prior to randomization; reductions in dose during the screening period are allowed. Subjects who are not already receiving a corticosteroid at time of randomization will not start corticosteroid treatment.

Subjects entering the study on an allowed non-steroidal IST must have been on the drug continuously for  $\geq$  6 months with no dose increase in the 4 months prior to randomization. Subjects will remain on the same dose of non-steroidal IST for the duration of the RCP unless dose reduction is deemed necessary for safety reasons. Azathioprine, mycophenolate mofetil, and mycophenolic acid are allowed non-steroidal ISTs. Tacrolimus is allowed in Japan only since it is the standard of care for treatment of MG in Japan.

Subjects on a stable dose of acetylcholinesterase inhibitors (pyridostigmine dose  $\leq$  480 mg/day) will be allowed to enroll. The acetylcholinesterase inhibitor dose must have been stable for at least 2 weeks prior to randomization. The acetylcholinesterase inhibitor dose must remain stable throughout the RCP unless dose reduction is deemed necessary for safety reasons. No increase in acetylcholinesterase inhibitors will be allowed in the study. Acetylcholinesterase inhibitors must be held for at least 6 hours prior to every study visit so that objective testing can be performed without the confounding effect of the acetylcholinesterase inhibitor.

Please refer to the exclusion criteria in [Section 5.2](#) for a list of medications that are not allowed during study. In addition, immunosuppressive medications other than those outlined in [Section 5.1](#), Inclusion Criterion #7, are prohibited unless agreed upon following consultation with the Sponsor medical monitor. Please keep in mind that several medications allowed as continuous, if they were started prior to study entry and were kept at stable dosing for a certain period of time, may not be allowed as newly prescribed drugs during study.

During the SFUP:

- Receipt of medications that target B cells or immunoglobulins during the SFUP requires immediate withdrawal from the SFUP. This includes any immunomodulatory or immunosuppressive drugs which have a pharmacodynamic effect on B cells and/or immunoglobulins (eg, rituximab, ocrelizumab, ofatumumab, obinutuzumab, or any experimental B cell depleting or modulating agent).
- Receipt of other protocol-defined prohibited medications (Section [7.5.1](#)), such as azathioprine or mycophenolate mofetil during the SFUP must be discussed with the Sponsor to determine whether the subject may continue participation in the SFUP.

## 8 SAFETY ASSESSMENT

### 8.1 Definitions

- **Adverse event** – An AE is any untoward medical occurrence associated with the use of an intervention in humans, whether or not it is considered intervention-related. MG exacerbations are an endpoint in this study and, therefore, will not be recorded as AEs or SAEs (with the exception of exacerbations that involve myasthenic crisis or death).
- **Serious adverse event** – An SAE is considered “serious” if, in the view of either the Investigator or Sponsor, it results in any of the following outcomes:
  - Death.
  - A life-threatening AE. An event is considered “life-threatening” if, in the view of either the Investigator or Sponsor, its occurrence places the patient or subject at immediate risk of death. It does not include an AE or suspected adverse reaction (SAR) that, had it occurred in a more severe form, might have caused death.
  - Inpatient hospitalization or prolongation of existing hospitalization. Any hospitalization requiring admission will be considered an inpatient hospitalization. An emergency room or urgent care visit without hospital admission will not be recorded as an SAE under this criterion, nor will hospitalization for a procedure scheduled or planned before signing of informed consent, or elective treatment of a preexisting condition that did not worsen from baseline. However, unexpected complications and/or prolongation of hospitalization that occur during elective surgery should be recorded as AEs and assessed for seriousness. Admission to the hospital for social or situational reasons (ie, no place to stay, live too far away to come for hospital visits, respite care) will not be considered inpatient hospitalizations.
  - A persistent or significant incapacity or substantial disruption of the ability to conduct normal life functions.
  - A congenital anomaly/birth defect.
  - Important medical events that may not result in death, be life-threatening, or require hospitalization may be considered serious when, based upon appropriate medical judgment, they may jeopardize the patient or subject and may require medical or surgical intervention to prevent 1 of the outcomes listed in this definition. Examples of such medical events include allergic bronchospasm requiring intensive treatment in an emergency room or at home, blood dyscrasias or convulsions that do not result in inpatient hospitalization, or the development of drug dependency or drug abuse.
- **Causality or relatedness** – The Investigator is required to provide an assessment of the relationship of AEs and SAEs to the IP. An event will be considered “not related” to use of IP if any of the following tests are met:
  - An unreasonable temporal relationship between administration of the IP and the onset of the event (eg, the event occurred either before or too long after administration of the IP for it to be considered IP-related).
  - A causal relationship between the IP and the event is biologically implausible (eg, death as a passenger in an automobile accident).

- A clearly more likely alternative explanation for the event is present (eg, typical adverse reaction [AR] to a concomitant drug and/or typical disease-related event).

Individual AE/SAE reports will be considered “related” to use of the IP if the “not related” criteria are not met.

“Related” implies that the event is considered to be “associated with the use of the drug” meaning that there is “a reasonable possibility” that the event may have been caused by the product under investigation (ie, there are facts, evidence, or arguments to suggest possible causation).

- **Adverse reaction** – An AR is any AE caused by a drug.
- **Suspected adverse reaction** – An SAR is any AE for which there is a reasonable possibility that the drug caused the AE. For the purposes of Investigational New Drug (IND) safety reporting, “reasonable possibility” means there is evidence to suggest a causal relationship between the drug and the AE. SAR implies a lesser degree of certainty about causality than AR.
- **Unexpected** – An event is considered unexpected if it is not listed in the Investigator’s Brochure, is not listed at the specificity or severity that has been observed, or, if an Investigator’s Brochure is not required or available, is not consistent with the risk information described in the General Investigational Plan or elsewhere in the IND. Unexpected also refers to events that are mentioned in the Investigator’s Brochure as occurring with a class of drugs or as anticipated from the pharmacological properties of the drug but are not specifically mentioned as occurring with the particular IP.
- **Severity or intensity** – Severity will be graded according to the Common Terminology Criteria for Adverse Events (CTCAE, version 5.0). The determination of severity for events not listed in the CTCAE should be made by the Investigator based upon medical judgment and the severity categories of Grade 1 to Grade 5 as defined below:
  - Grade 1 (mild): An event of mild intensity that is usually transient and may require only minimal treatment or therapeutic intervention. The event does not generally interfere with usual activities of daily living.
  - Grade 2 (moderate): An event of moderate intensity that is usually alleviated with additional, specific therapeutic intervention. The event interferes with usual activities of daily living, causing discomfort, but poses no significant or permanent risk of harm to the subject.
  - Grade 3 (severe): A severe event that requires intensive therapeutic intervention. The event interrupts usual activities of daily living, or significantly affects the clinical status of the subject.
  - Grade 4 (life-threatening): An event, and/or its immediate sequelae, that is associated with an imminent risk of death or with physical or mental disabilities that affect or limit the ability of the subject to perform activities of daily living (eating, ambulation, toileting, etc.).
  - Grade 5 (fatal): Death (loss of life) as a result of an event.

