### 2.1.5 Anticipated Study Benefits and Risks

This study has been designed to minimize risks to subjects where possible. The risks of study participation include the risks of inebilizumab that are summarized in [Section 2.1.4](#) and the Investigator's Brochure, risk of worsening of MG, and risk of loss of privacy. In prior clinical trials, inebilizumab was found to have an acceptable risk profile with a convenient dosing regimen and a low rate of IRRs. Subjects are allowed to use selected standard of care MG treatments during the study. Those treatments can be continued during the RCP with the exception of corticosteroids, which are tapered to prednisone 5 mg/day to reduce the potential risk and morbidity associated with long-term use of moderate- or high-dose corticosteroids. If symptoms worsen during the study, rescue therapy is allowed. The study inclusion and exclusion criteria reduce the risk to subjects by excluding those who may be at elevated risk of complications from the use of inebilizumab (eg, those with chronic infections or baseline cytopenia). The criteria for required discontinuation of the IP ([Section 6.3.1](#)) were designed to stop the IP in anyone for whom continued use may be an unjustified risk. An OLP is included in the study to ensure that all study subjects who complete the RCP have the opportunity to receive open-label inebilizumab.

The benefits of study participation include potential receipt of an IP that may reduce MG-related disability. This hypothesis is based on data from multiple case series showing that B-cell depletion with rituximab, a drug with a similar mechanism of action to inebilizumab, can improve outcomes in refractory MG subjects ([Iorio et al, 2015](#)). The subjects who will enter the study have moderate to severe MG symptoms despite use of standard of care treatments, including azathioprine, mycophenolate mofetil, mycophenolic acid, tacrolimus (Japan only), and/or corticosteroids. The potential benefits to subjects and society of testing the hypothesis that inebilizumab can reduce MG-related disability are believed to outweigh the potential risks.

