**Table 6 Safety Follow-up Period**

Study Period	Safety Follow-up
Safety Follow-up Weeks	Every 26 weeks from time subject completes treatment/discontinues IP (up to 2 years)
Visit Window	± 4 weeks
Assessment of AEs and SAEs	X
Assessment of concomitant medications	X
Hematology and serum chemistry	X
Blood collection for: [REDACTED]	X

AE = adverse event; [REDACTED]; IP = investigational product; SAE = serious adverse event.

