#### 6.1.5 Special Visit Types (occurring during RCP and OLP)

##### 6.1.5.1 Remote Visits and/or Procedures

In exceptional circumstances and with prior agreement of the medical monitor, particular study visits or procedures may be performed remotely (via teleconference, video conference, or similar) if the subject is not able to physically attend the clinic for that visit or procedure (eg, due to COVID-19 restrictions). Missed assessments during remote visits, regardless of medical monitor agreement, will incur protocol deviations. Refer to [Table 7](#).

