#### 9.4.3 Analysis of Additional Secondary Efficacy Endpoints

The additional secondary efficacy endpoints include:

1. The proportion of subjects with  $\geq 3$ -point improvement in MG-ADL score at Week 26 and no use of rescue therapy between Day 28 and Week 26 in the overall study

- population, the AChR-Ab+ population, and the MuSK-Ab+ population, and at Week 52 and no use of rescue therapy between Day 28 and Week 52 in the AChR-Ab+ population.
2. Change from baseline in MG-ADL score at Week 52 in the AChR-Ab+ population.
  3. Change from baseline in QMG score at Week 52 in the AChR-Ab+ population.
  4. Change from baseline in MGC score at Week 26 and no use of rescue therapy between Day 28 and Week 26 in the overall study population, the AChR-Ab+ population, and the MuSK-Ab+ population, and at Week 52 and no use of rescue therapy between Day 28 and Week 52 in the AChR-Ab+ population.
  5. Change from baseline in MGQOL-15r score at Week 26 in the overall study population, AChR-Ab+, and MuSK-Ab+ and at Week 52 in AChR-Ab+ Week 26 in the overall study population, the AChR-Ab+ population, and the MuSK-Ab+ population and at Week 52 in the AChR-Ab+ population.
  6. PGIC score at Week 26 in the overall study population, the AChR-Ab+ population, and the MuSK-Ab+ population and at Week 52 in the AChR-Ab+ population.
  7. Time to first MG exacerbation by Week 26 in the overall study population, the AChR-Ab+ population, and the MuSK-Ab+ population and by Week 52 in the AChR-Ab+ population. Where an exacerbation is defined as one of the following:
    - Use of protocol-defined rescue therapy, or
    - Myasthenic crisis, defined as worsening of myasthenic weakness requiring intubation or noninvasive ventilation to avoid intubation, except when these measures are employed during routine postoperative management, or
    - Significant symptomatic worsening to a score of 3 or a 2-point increase from baseline on any one of the individual MG-ADL items other than double vision or eyelid droop.
  8. The safety and tolerability of inebilizumab as measured by the incidence of TEAEs, AESIs, and TESAEs. Laboratory measurements will also be evaluated as part of safety
  9. The proportion of subjects with steroid tapered to  $\leq 5$  mg/day at Week 26 for the overall study population, the AChR-Ab+ population, and the MuSK-Ab+ population and at Week 52 for the AChR-Ab+ population.

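### The AE/SAE exemption for MG exacerbations has no time limit, so a non-crisis, non-fatal exacerbation in the safety follow-up is recorded neither as an adverse event nor as an endpoint event

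*Protocol*

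**What the plan says.** - **The exemption.** In its definition of an adverse event, Protocol 8.1 states that "MG exacerbations are an endpoint in this study and, therefore, will not be recorded as AEs or SAEs". A single carve-out follows in parentheses: "with the exception of exacerbations that involve myasthenic crisis or death". The rule names no study period and does not refer to another section for the meaning of exacerbation.
- **What the exception covers.** Protocol 9.4.3 gives the only definition: "Myasthenic crisis, defined as worsening of myasthenic weakness requiring intubation or noninvasive ventilation to avoid intubation", with routine postoperative use left out.
- **Hospital admission.** For SAEs, 8.1 also says "Any hospitalization requiring admission will be considered an inpatient hospitalization".
- **The endpoint.** Item 7 of 9.4.3 is "Time to first MG exacerbation by Week 26 in the overall study population" and in each antibody population, and by Week 52 in AChR-Ab+ subjects. SAP 3.4.5 agrees. Both times lie inside the RCP.
- **AE collection.** Protocol 8.3 runs it from consent to the end of the study.
- **The SFUP.** Protocol 6.1.4 puts all subjects into it after the last dose, for up to 2 years or until B-cell recovery (with a further, redacted condition) if that is sooner. Table 6 lists AEs/SAEs, concomitant medications, hematology and chemistry, and a partly redacted blood collection, at visits 26 weeks apart. No MG-ADL, QMG, MGC or MGFA row appears.
- **Clinical Deterioration Visits.** The heading of 6.1.5 confines the special visit types to the RCP and OLP.

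**The concern.** Taking an efficacy event out of AE reporting is ordinary practice when the event is captured elsewhere. Here the justification is that exacerbation is an endpoint, and in the SFUP it is not one. The exemption nevertheless continues for as long as AEs are collected.

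The protocol itself gives reason to want these events. Section 2.1.5 lists "risk of worsening of MG" among the risks of participation. The background in 2.1 describes relapse in AChR-Ab+ subjects after another B-cell-depleting antibody, within an average of 3 years after treatment. The SFUP is the part of the study that follows subjects longest after their last dose.

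SAP 3.4.1 and 3.5 build the follow-up safety summaries from the data captured in that period. An admission that the recording rule excludes cannot appear there. It also escapes the 24-hour SAE report in Protocol 8.3 and the investigator's severity and causality assessment.

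**Working it through.** The plan states no figure on this point. The check is a cross-reading, followed by the length of the uncovered time.

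**1. How each criterion of the 9.4.3 definition works in the SFUP**
- *Rescue therapy.* Protocol 7.2.2 does not limit rescue (IVIg or PLEX) to a period. Two of its three triggers need a QMG score, which the SFUP does not collect. The third, the investigator's concern for the subject's health, can still apply. A rescued worsening is therefore a defined exacerbation, and exempt unless it involves crisis or death.
- *Myasthenic crisis.* Recorded, under the exception in 8.1.
- *Worsening on an MG-ADL item.* Cannot be scored, because Table 6 has no MG-ADL.

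**2. A worked case.** A subject in the SFUP is admitted with worsening MG, is not ventilated, receives IVIg and recovers. The admission would meet the hospitalization criterion, but 8.1 removes the event from AE/SAE recording. It falls after Week 26 or 52, so it is not an endpoint event. No MG scale is scheduled and no Clinical Deterioration Visit applies. What remains is a concomitant medication entry (Table 6) and possibly a rescue-therapy eCRF page (7.2.2). SAP 3.3.4 plans concomitant medication summaries for the RCP and the OLP and names none for the follow-up period.

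**3. Length of the uncovered time**
Inputs: dosing days and last visits with MG scores from Protocol Tables 3, 4, 5 and 8; SFUP length of 104 weeks after the last dose from the Synopsis.

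Week = (Day − 1) / 7. Gap = (week of last dose + 104) − week of last MG score.
- AChR-Ab+, completes the RCP, skips the OLP: last dose Day 183 = Week 26; last score Day 365 = Week 52; gap = 26 + 104 − 52 = **78 weeks**.
- MuSK-Ab+, completes the RCP, skips the OLP: last dose Day 15 = Week 2; last score Day 183 = Week 26; gap = 2 + 104 − 26 = **80 weeks**.
- OLP completer: last dose OLP Day 911 = Week 130; last score OLP Day 1093 = Week 156; gap = 130 + 104 − 156 = **78 weeks**.

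Counting 730 days instead of 104 weeks (728 days) adds 2 days to each. For a subject who stops treatment during the OLP, scores end at the early discontinuation visit, so the gap is 104 weeks less the time from last dose to that visit.

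**4. What shortens it.** The SFUP may end on B-cell recovery (6.1.4). Protocol 7.5.2 also requires immediate withdrawal from the SFUP when a subject receives a drug acting on B cells or immunoglobulins. A relapse treated that way could end follow-up without an exacerbation event on record.

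**The case against.** The best counter-argument is definitional. If exacerbation in 8.1 means exactly what 9.4.3 says, then a follow-up worsening treated without IVIg or PLEX, and without crisis, meets no criterion that can be scored. It is then not an exempt exacerbation, and the ordinary AE and hospitalization rules apply. One can also read the exemption as lapsing once the event cannot be an endpoint. This narrows the gap but does not close it: an admission treated with IVIg or PLEX meets the first 9.4.3 criterion and stays exempt. Nor does 8.1 cite 9.4.3 or state that it lapses, so a site may well apply the everyday meaning of exacerbation.

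Three stronger readings are tempting, and the documents do not support them.
- *Hospitalized MG worsening after stopping drug leaves no record at all.* Crisis and fatal events are recorded, and treatment leaves an entry. Subjects who stop treatment in the RCP are asked to complete the RCP assessments (6.3.1), and OLP completers are scored for 26 weeks after their last dose.
- *The OLP has the same gap.* The endpoint does end before the OLP, but MG-ADL is scored at every OLP visit and Clinical Deterioration Visits apply there. A separate OLP rule would also mix two definitions in the combined RCP and OLP tables.
- *The study loses about 345 person-years.* That figure is 230 × 548 / 365.25, with 548 days being 911 + 730 − 1093. It assumes that all 230 subjects stay for the full period, with no exit under 6.1.4 or 7.5.2, and 230 is itself an upper limit (4.1).

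**Conclusion.** The point stands for the SFUP only. The exemption in 8.1 outlasts its stated reason, so non-crisis, non-fatal exacerbations in that period, including those needing admission, are recorded neither as AEs/SAEs nor as endpoint events. Their treatment may be visible, but without seriousness, severity or causality.

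The uncovered time is at most 78 weeks per subject (OLP completers, and AChR-Ab+ subjects who complete the RCP only) or 80 weeks (MuSK-Ab+ subjects who complete the RCP only). These are maxima. The documents give no rate of exacerbation after the last dose, so the number of missed events cannot be estimated.

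Two assumptions apply. First, the redactions hide no MG measure in the SFUP; the visible one in Table 6 is in the blood-collection row, but the exploratory endpoints cannot be seen. Second, the extent depends on how 8.1 is read: on the strict 9.4.3 definition the loss is confined to exacerbations treated with IVIg or PLEX, and on the everyday meaning it covers every exacerbation short of crisis or death.

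The change log suggests a carry-over: it lists the exemption under Version 5.0, the follow-up section as new under Version 6.0, and mandatory follow-up under Version 9.0.

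**What to change.** Reconcile Protocol 8.1 with 6.1.4 and Table 6, 8.3 and 9.4.3:
- Limit the exemption to the RCP and OLP, where MG scores and Clinical Deterioration Visits capture exacerbations.
- State that in the SFUP an MG exacerbation is recorded as an AE, or as an SAE when a seriousness criterion such as hospitalization is met. Because MG-ADL is not scored there, say that the investigator's judgment identifies the event.
- In SAP 3.5, tabulate these events under their own preferred term in the follow-up summaries.

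This changes recording only, not clinical management, and leaves the primary and key secondary analyses untouched. The cost is a sentence or two in 8.1, a table line, and some additional AE/SAE reports in the SFUP. AE rates for that term in the SFUP will not be directly comparable with RCP or OLP rates, and a table footnote should say so. No change to the OLP recording rule is needed.
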